## 432 **9. Device Issues**

433

434 Reported device issues for each type of study device (e.g., closed loop system, CGM, blood  
435 glucose meter)

436

437

## 438 **10. Protocol Adherence and Retention**

439

440 The following tabulations and analyses will be performed by treatment group to assess protocol  
441 adherence for the study:

442

- 443 • Listing of all protocol deviations
- 444 • Tabulation of protocol-specified visits and phone contacts completed in window, out  
of window and missed for each visit/phone contact
- 445 • Flow chart accounting for all enrolled participants up to randomization

446           • Flow chart of all randomized participants at all scheduled visits and phone contacts to  
447           assess visit, and phone completion, and study completion rates  
448           • Number of and reasons for unscheduled visits and phone calls  
449           • Number of participants who stopped treatment (CLC or CGM) and reasons  
450

451

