407 408 409	Study participants will be recruited from 7 clinical centers in the United States without regard to gender, race, or ethnicity. There is no restriction on the number of participants to be enrolled by each site toward the overall recruitment goal.
410 411	A study goal will be to have the following minimum numbers of participants complete the trial in the specified subgroups at the time of enrollment:
412	• At least 50 participants with HbA1c ≥7.5% and 50 participants with HbA1c <7.5%
413	• At least 50 participants in the age range 14 to <26 and 50 participants ≥26 years old
414	• At least 30 participants who are on multiple daily injections (MDI) rather than pump
415 416	 At least 30 participants who are CGM-naïve (defined as not using a CGM in the prior 14 days)
417	2.1.1 Informed Consent and Authorization Procedures
418 419 420	Potential eligibility may be assessed as part of a routine-care examination. Before completing any procedures or collecting any data that are not part of usual care, written informed consent will be obtained.
421 422 423 424 425	For potential study participants ≥18 years old, the study protocol will be discussed with the potential study participant by study staff. The potential study participant will be given the Informed Consent Form to read. Potential study participants will be encouraged to discuss the study with family members and their personal physicians(s) before deciding whether to participate in the study.
426 427 428 429 430 431 432	For potential participants under 18 years of age, a parent/legal guardian (referred to subsequently as "parent") will be provided with the Informed Consent Form to read and will be given the opportunity to ask questions. Potential participants meeting the IRB's minimum age of assent will be given a Child Assent Form to read and discuss with his/her parents and study personnel. If the parent and child agree to participate, the Informed Consent Form and Child Assent Form will be signed. A copy of the consent form will be provided to the participant and his/her parent and another copy will be added to the participant's study record.

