750 751	Participants will be instructed to download the study device prior to each phone visit or on at least every 4 week basis throughout the remainder of the study.
752	5.1.4 1-Week Phone Contact
753 754	Study staff will perform a phone call with the participant within 7 (± 1) days following randomization.
755	The following will occur:
756	Assessment of compliance with study device use by review of any available device data
757	• Assessment of adverse events, adverse device effects, and device issues
758	 Study staff will answer any questions related to device use
759 760	Participants will then complete an additional week of home use with the study system. Participants will return to clinic 14 (±3) days from the date of randomization.
761	5.1.5 2-Week Visit (Training Review and Insulin Pump Optimization)
762 763	The participant will be offered review training to address any questions on the use of the study device including meal bolus strategies and strategies related to pump use and exercise.

D981-FF58-4975-AEFF PAGE 34 OF 74

764	The following will occur:
765	• Assessment of compliance with study device use by review of any available device data
766	 Assessment of adverse events, adverse device effects, and device issues
767 768 769	• Study staff will answer any questions related to device use and follow the procedure for insulin pump optimization described in section 3.2 using the study CGM available data from the previous two weeks.
770 771	• The study blood glucose meter and study ketone meter will be downloaded and QC tested with at least two different concentrations of control solution if available.
772	5.2 Procedures for the SAP Group
773 774 775 776 777	Participants in the SAP group will use an insulin pump with no automated insulin delivery in conjunction with the study CGM, study blood glucose meter and study ketone meter. Participants not already using an insulin pump with no automated insulin delivery at enrollment will be provided with a study pump to use. Study pump training and/or study CGM training will be provided if the participant is initiating use of these devices at this point.
778 779 780	Participants may use available manufacturer-provided software and features of the study CGM related to mobile data access or remote monitoring, but will be instructed not to use any third-party components for this purpose.
781	5.2.1 Study Device Data Download

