1515	 BG-measured hyperglycemic events (one BG record >350 mg/dL) 		
1516	 Worsening of HbA1c from baseline to 26 weeks by >0.5% 		
1517	• Other serious adverse events (SAE) and serious adverse device events (SADE)		
1518	• Adverse device effects (ADE)		
1519	 Unanticipated adverse device effects (UADE) 		
1520 1521	For the following outcomes, mean \pm SD or summary statistics appropriate to the distribution will be tabulated by treatment group:		
1522	• Number of SH events and SH event rate per 100 person-years		
1523	• Number of DKA events and DKA event rate per 100 person-years		
1524	• Any adverse event' rate per 100 person-years		

D981-FF58-4975-AEFF PAGE 62 OF 74

1525 1526 1527 1528	If enough events, the numbers will be compared between the two treatment arms using a robust Poisson regression. The regression will adjust for the participant-reported number of events prior to the start of the study and site as random effect. The amount of follow up will be included as an offset covariate to compare the rates.
1529 1530	Comparison of safety outcomes between the two treatment groups only include those events occurring on or after randomization until the 26 week visit.
1531 1532	Any pre-randomization adverse events will be tabulated separately and will include participants who were never randomized.
1533	10.9 Intervention Adherence
1534 1535	The following tabulations and analyses will be performed by treatment group to assess intervention adherence for the study:
1536	• Sensor use – hours of use and percent time of use
1537	• The daily frequency of downloaded BGM use
1538	For CLC arm only, the following will be tabulated to assess adherence:
1539	• % time in different operational modes per week - overall and by month
1540	10.10 Adherence and Retention Analyses
1541 1542	The following tabulations and analyses will be performed by treatment group to assess protocol adherence for the study:
1543 1544	 Number of protocol and procedural deviations per participant along with the number and percentage of participants with each number of deviations
1545	• Number of protocol and procedural deviations by severity with brief descriptions listed
1546 1547	• Flow chart accounting for all participants at all scheduled visits and phone contacts post treatment initiation to assess visit and phone completion rates
1548	 Number of and reasons for unscheduled visits and phone calls
1549	 Number of participants who stopped treatment and reasons

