**Study PI Approver:**

34 **1. Study Overview**

35  
36 This document outlines the statistical analyses to be performed for the Original DCLP3 Trial and  
37 to be included in the primary manuscript data packet.

38  
39 The following table excerpted from the protocol gives an overview of the study.

40  
41 **Table 1. Study Overview**

42

PARTICIPANT AREA	DESCRIPTION
Title	The International Diabetes Closed Loop (iDCL) Trial: Pivotal Trial of t:slim X2 with Control-IQ Technology
Précis	A randomized controlled trial of 6 month at home closed loop system vs. sensor-augmented pump.
Investigational Device	t:slim X2 with Control-IQ and Dexcom G6 system
Objectives	The objective of the study is to assess efficacy and safety of a closed loop system (t:slim X2 with Control-IQ Technology) in a large randomized controlled trial.
Study Design	Randomized Clinical Trial with 2:1 randomization to intervention with the closed loop system vs. sensor-augmented pump for 6 months.
Number of Sites	Seven US clinical sites
Endpoint	The primary outcome is time in target range 70-180 mg/dL measured by CGM in CLC group vs. SAP group at 6 months
Population	Key Inclusion Criteria 

• Type 1 Diabetes

• Ages 14 and older

 Key Exclusion Criteria 

• Use of any non-insulin glucose-lowering agents except metformin

Sample Size	Up to seven clinical sites in the United States may enroll up to 225 total participants with the goal of randomizing 168 participants such that at least 150 participants complete the 6-month randomized trial.
Treatment Groups	Randomized Trial 

• Intervention Group: t:slim X2 with Control-IQ Technology and Study CGM.

• Control Group: Sensor-augmented pump (SAP) with no automated insulin delivery, and study CGM

Participant Duration	6-8 months

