### 222 223       5.2 Analysis Cohorts

#### 224 225       Primary and Secondary Analyses:

- 226       • All randomized participants will be analyzed according to the ITT principle as described  
 227       above.
- 228       • All randomized subjects with a lab or local HbA1c measurement at 13 or 26 weeks will be  
 229       included in HbA1c analyses. Similar approaches will be followed for the other secondary  
 230       outcomes like insulin, weight, and questionnaires analyses.

231

232 Per Protocol (PP) Analyses:

233 Four different per protocol analyses will be considered:

- 234 • If more than 5% of subjects in a treatment group have fewer than 168 hours of post-randomization CGM data, the primary and secondary hierarchical analyses will be replicated excluding such subjects.
- 235 • If more than 5% of subjects in a treatment group have fewer than 2,184 hours of post-randomization CGM data, the primary and secondary hierarchical analyses will be replicated excluding such subjects.
- 236 • The primary and secondary hierarchical analyses will be replicated only with participants from CLC group who used the system in CL mode for >3,494 hours overall and with participants from SAP group who used the sensor for >3,494 hours overall.
- 237 • The first 2 weeks in the CLC group involve system training. The primary and secondary hierarchical CGM analyses will be repeated excluding CGM data prior to the 2-week visit date (or Day 14 post-randomization, if the 2 week visit is missing). Only subjects with at least 24hr of CGM data following the first 2 weeks will be included in this analysis.

248

249 Safety Analyses:

- 250 • Safety outcomes will be reported for all randomized participants by treatment arm. Separately, any reported adverse events during the pre-randomization phase will be tabulated.

253

254 Sensitivity Analysis:

- 255 • Covariate adjustment: As noted below in Section 6, the primary and secondary hierarchical analyses will include a pre-specified list of covariates. Imbalances between groups in important covariates (as specified below in Section 11) are not expected to be of sufficient magnitude to produce confounding. However, the presence of confounding will be evaluated by additionally including factors potentially associated with the outcome for which there is an imbalance between groups (assessed based on clinical judgement reviewing the distributions in the two treatment arms, not on a p-value).

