572           For comparison of other efficacy endpoints considered exploratory, the false discovery rate  
573           (FDR) will be calculated using the Benjamini-Hochberg method adapted using the two-stage  
574           test. FDR adjusted p-values will be calculated separately for the following categories:

575           • CGM metrics over 24hr  
576           • CGM metrics during awake periods  
577           • CGM metrics during nighttime periods  
578           • CGM metrics during the first three months  
579           • HbA1c analyses  
580           • Insulin, weight, BMI  
581           • Questionnaires  
582           • Subgroup analyses (separately for each primary and secondary hierarchical outcomes  
583           found significant)

584  
585  
586           P-values from safety analyses, sensitivity analyses and per-protocol analyses will not be adjusted  
587           for multiple comparisons.

590                   **16. Exploratory analyses**

591

592   No p-values will be calculated for these analyses.

593

594   The following metrics will be reported with the appropriate statistics by the associated CL mode:

595                   • % below 70 mg/dL

596                   • % above 180 mg/dL

597                   • % time in range 70-180 mg/dL

598                   • mean glucose

599                   • coefficient of variation

600

601

602                   **17. Additional Tabulations and Analyses**

603

- 604                  • 24 hours profiles with mean (or medians) and quartiles lines and 4-week interval boxplots  
605                  by treatment arms for:

606                    ○ % below 70 mg/dL

607                    ○ % above 180 mg/dL

608                    ○ % time in range 70-180 mg/dL

609                    ○ mean glucose

610                    ○ coefficient of variation

- 611                  • Subjects in the CLC arm will enter their bedtimes in the system. Summary statistics for  
612                  the same outcome metrics listed in the previous bullet will be given stratified by sleep and  
613                  awake times.

- 614                  • It is expected to collect most of the continuous insulin data in the two treatment groups  
615                  over 26 weeks. The two insulin analyses (total daily insulin per kg and basal: bolus insulin  
616                  ratio based on the subject-reported values) will be repeated using 2 weeks of system  

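### The stopped-treatment count in SAP Section 10 leaves out the control-arm pump, and the third per-protocol cohort has no pump condition for controls (minor)

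*SAP*

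**What the plan says.** In what follows, SAP means the statistical analysis plan, and the sensor-augmented pump group is called the control arm.

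- **Control treatment.** Protocol 5.2 states: "Participants in the SAP group will use an insulin pump with no automated insulin delivery in conjunction with the study CGM". The overview table in SAP Section 1 describes the control group in the same way: "Sensor-augmented pump (SAP) with no automated insulin delivery, and study CGM".
- **Count of stopped treatment.** Protocol 10.10 lists "Number of participants who stopped treatment and reasons", with no device named. SAP Section 10 lists "Number of participants who stopped treatment (CLC or CGM) and reasons".
- **Third per-protocol analysis.** SAP 5.2 keeps CLC participants with more than 3,494 hours in closed-loop mode and "participants from SAP group who used the sensor for >3,494 hours overall". Protocol 10.5.1 has the same structure, expressed as more than 80% of closed-loop or sensor use.
- **Adherence tables.** SAP Section 12 tabulates sensor use and meter frequency by arm as intervention adherence. Time in each operational mode is tabulated for the CLC arm only.
- **Pump data.** SAP Section 17 says "It is expected to collect most of the continuous insulin data in the two treatment groups" and planned to repeat the insulin analyses from system or pump data. Item 1 of the May 2019 addendum replaces those analyses and uses CRF insulin data for the control arm.

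**The concern.** The trial compares closed loop with sensor-augmented pump therapy. A reader of the results will want to know how many controls stayed on a pump, and will look for this in the stopped-treatment count and the adherence table. The SAP wording points both of these at the sensor. It also treats the arms differently. In the CLC arm, giving up the pump ends closed-loop control and is therefore counted. In the control arm, giving up the pump while still wearing the sensor falls outside the parenthesis.

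The third per-protocol analysis has the same asymmetry. Adherence means use of the whole treatment in one arm and of one component in the other. A per-protocol result is read as the contrast among people who took what they were assigned, and for the controls this rule does not ensure that.

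The situation is foreseeable. Protocol 2.1 sets a goal of "At least 30 participants who are on multiple daily injections (MDI) rather than pump" among those completing the trial, so some controls will be new to pump therapy. Protocol 8.5.1 encourages participants who stop the study device system to remain in the study.

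**Working it through.** The check is mainly a comparison of rules, with three short calculations.

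**1. The hour threshold (SAP 5.2).** Follow-up is 26 weeks: 26 × 7 × 24 = 4,368 hours. Then 0.80 × 4,368 = 3,494.4, which reproduces the SAP's 3,494 and matches the 80% in Protocol 10.5.1. The second per-protocol threshold, 2,184 hours, is 0.50 × 4,368. In the control arm both are rules about sensor or CGM time only.

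**2. The other per-protocol analyses.** The first two (168 and 2,184 hours) depend on CGM data in both arms. The fourth drops the first two weeks of CGM data. None of the four has a pump condition for controls.

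**3. Following each rule for a participant who stops the pump early and keeps wearing the sensor.**

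| Rule | CLC arm | Control arm |
|---|---|---|
| SAP 10 stopped-treatment count | Counted, because closed loop stops with the pump | Not counted |
| Protocol 10.10 stopped-treatment count | Counted | Counted on a plain reading |
| SAP 12 adherence tables | Visible in operational-mode time | Not visible; sensor and meter only |
| Third per-protocol cohort | Dropped, because closed-loop hours cease to accrue | Kept if sensor use exceeds 3,494 hours |
| Deviation listing (SAP 10) | May appear | May appear |

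Timing matters in the CLC column. The threshold leaves 4,368 − 3,494 = 874 hours, about 36 days (874 / 24 = 36.4), so a CLC participant with otherwise complete use who stops in the last five weeks would also be kept. The asymmetry concerns earlier stops.

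**4. Weight of one participant.** With 168 randomized 2:1, the control arm is 168 / 3 = 56. One participant is 1 / 56 = 1.8% of that arm.

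**5. Sample size.** The planned minimum reproduces. With a difference of 7.5, SD 12, two-sided 5% error, 90% power and 2:1 allocation, the control arm needs 41, so 41 + 82 = 123. Nothing proposed here changes that figure.

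**6. What cannot be computed.** The documents give neither a rate of pump discontinuation nor a difference in time in range between pump and injections. No effect on any estimate follows from them.

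**The case against.** The strongest reply is that a pump stop would not go unrecorded. The first item in SAP Section 10 is a listing of all protocol deviations, and Protocol 11.4 defines a deviation as any noncompliance with the protocol, by the participant included. Abandoning the pump departs from Protocol 5.2 and should be listed. That stands, and it rules out saying that the event would be invisible. But a listing is not a count of treatment stops with reasons, and it does not decide who is in the per-protocol set.

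A second reply is that the plan guards against the problem. Under Protocol 3.1, pump-naïve entrants must use the study pump each day in run-in and show competency. Under Protocol 4.1.3, nobody is to be randomized unless the investigator is convinced that they will accept either arm. This makes stops less likely, but does nothing to count those that occur.

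Third, the sensor-only criterion comes from Protocol 10.5.1, the analysis is one of four supportive ones, and no success criterion depends on it. All of that is true, and it limits the weight of the point.

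A reader might go further and infer that uncounted pump stops lower the control mean and inflate the primary treatment effect. The documents do not support this. The primary analysis follows assignment whatever devices are used, so such changes are part of what it estimates, and rewording the count would not move it. Nor can the goal of 30 participants on injections serve as a stop rate. It describes completers by their regimen at enrollment and says nothing about who returns to injections.

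**Conclusion.** The point holds, as a minor one. SAP Section 10 is narrower than Protocol 10.10 and omits one of the two components of the control treatment. The third per-protocol cohort requires closed-loop hours in one arm and only sensor hours in the other. Followed as written, these rules leave a control who stopped the pump out of the stopped-treatment count and, with more than 3,494 sensor hours, in the per-protocol set.

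The consequence is confined to adherence reporting and that one supportive analysis. The intention-to-treat primary analysis stays valid and unchanged. No size can be given beyond 1.8% of the control arm per affected participant, which assumes 56 controls. The conclusion rests on reading the parenthesis in Section 10 literally, and on the participant continuing to wear the sensor after stopping the pump.

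**What to change.** 1. In SAP Section 10, replace the item with: *stopped treatment (CLC arm: closed loop, pump or CGM; control arm: pump or CGM) and reasons*. This restores the scope of Protocol 10.10.
2. In the third per-protocol analysis of SAP 5.2, also exclude control participants with a documented pump stop. Say that this means a lasting discontinuation, since the CLC criterion itself tolerates some time out of closed loop. Record the change as an addition to Protocol 10.5.1, which has the same sensor-only rule.
3. Identify stops from visit or CRF records. Use the pump downloads in Protocol 5.3.1.1 as support only. Controls may be on personal pumps, and a missing upload can look like non-use, so a measure based on days with uploaded data could wrongly remove genuine pump users.

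The cost is two wording changes, a small amount of record checking, and possibly a slightly smaller control per-protocol set. Sample size, power and the primary analysis do not change.

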## 452           **11. Baseline Descriptive Statistics**

453

454           Baseline demographic and clinical characteristics of the cohort of all randomized participants  
455           will be summarized in a table using summary statistics appropriate to the distribution of each  
456           variable. Descriptive statistics will be displayed overall and by treatment group.

457

458           Will include:

459           • Age  
460           • Gender  
461           • Race/ethnicity  
462           • Income, education, and/or insurance status  
463           • Diabetes duration  
464           • Insulin method before enrollment (pump vs. MDI)  
465           • CGM use before enrollment  
466           • Daily SMBG for CGM users and non-users  
467           • HbA1c  
468           • BMI  
469           • C-peptide  
470           • Scores for quality of life, hypoglycemia awareness, and fear questionnaires  
471           • Participant-reported number of SH and DKA 12 months prior to the start of the study  
472

473

